7.7.4. Subgroup Analyses

Subgroup analyses to be performed for EFS are presented in [Table 10](#).

Table 10: Subgroup Analyses to be Performed for EFS

Subgroup	Categories
De novo status based on IRT	Yes; No
De novo status based on Investigator from eCRF	Yes; No
Region	United States and Canada; Western Europe, Israel or Australia; Japan; ROW
Age	<75; ≥75 years
Baseline ECOG PS	0 or 1; ≥2
Sex	Female; Male
Race	White; Asian; Black or African American; Other (Other includes American Indian or Alaska Native, Native Hawaiian or other Pacific Islander, and not reported)
Baseline cytogenetic risk status	Favorable risk; Intermediate risk; Poor risk
WHO classification of AML	AML with genetic abnormalities; AML with myelodysplasia-related changes; Therapy-related myeloid neoplasms; AML not otherwise specified
Baseline WBC count	≤5×10 ⁹ /L; >5×10 ⁹ /L
Baseline percent bone marrow blasts*	≤50%; >50%

Abbreviations: AML = acute myelogenous leukemia; ECOG PS = Eastern Cooperative Oncology Group performance status; ROW = rest of world; WBC = white blood cell; WHO = World Health Organization.

*For bone marrow blasts, bone marrow aspirate will be used as the primary source. If a bone marrow aspirate assessment is not available, a bone marrow biopsy assessment will be used.

Treatment arms will be compared for EFS using a 2-sided unstratified log-rank test for each category and the unstratified HR and its corresponding 95% CI will be computed for each category and depicted in a forest plot.

If there is a low number of subjects within a category (<5% of the subjects in the FAS), the categories will be pooled (if 3 or more categories are pre-specified for the subgroup) or the subgroup will not be analyzed (if only 2 pre-specified categories in the subgroup). [REDACTED]

7.8. Safety Analyses

Summaries of safety data will be presented by treatment arm based on the safety analysis set.

7.8.1. Adverse Events

Treatment-emergent adverse events (TEAEs) are AEs with a first onset date during the on-treatment period or worsening from baseline. All summaries described below will be based on TEAEs, if not otherwise specified.

All AEs will be listed by subject and AEs with onset outside of the on-treatment period will be flagged in the listings. Unless otherwise specified, TEAEs will be summarized according

to the latest version of MedDRA by SOC and/or PT, severity (based on CTCAE v4.03 grading), seriousness, and relation to study treatment in decreasing frequency based on the frequencies observed for the AG-120+azacitidine arm.

Each subject will be counted only once within each SOC or PT. If a subject experiences multiple TEAEs under the same PT within a SOC for the same summary period, only the TEAE assessed as related or with the worst severity, as applicable, will be included in the summaries of relationship and severity. If a subject has TEAEs with missing and non-missing grades, the maximum of the non-missing grades will be displayed. No imputation of missing grades will be performed.

The following will be summarized:

- TEAEs by SOC and PT
- TEAEs by SOC, PT, and worst grade
- Most common TEAEs and Grade ≥ 3 TEAEs by PT; these will include TEAEs (any grade) reported in $\geq 10\%$ of subjects in either treatment arm or Grade ≥ 3 TEAEs reported in $\geq 5\%$ of subjects in either treatment arm. These thresholds may be changed based on the observed data without an amendment to this SAP.
- Treatment-related TEAEs, by SOC and PT
- Treatment-related TEAEs, by SOC, PT, and worst grade
- Grade ≥ 3 TEAEs, by SOC and PT
- Treatment-related Grade ≥ 3 TEAEs, by SOC and PT
- Serious TEAEs, by SOC and PT
- Treatment-related Serious TEAEs, by SOC and PT
- TEAEs leading to discontinuation of study drug, by SOC and PT
- TEAEs leading to interruption of study drug, by SOC and PT
- TEAEs leading to dose reduction, by SOC and PT
- TEAEs leading to death, by SOC and PT
- Treatment-related TEAEs leading to death, by SOC and PT

Treatment-related TEAEs (including TEAEs, Grade ≥ 3 TEAEs, serious TEAEs, and TEAEs leading to death) will be summarized separately for

- TEAEs related to AG-120/matched placebo only
- TEAEs related to azacitidine only
- TEAEs related to both AG-120/matched placebo and azacitidine

TEAEs leading to discontinuation of study drug, TEAEs leading to interruption of study drug, and TEAEs leading to dose reduction, will be summarized separately for

- AG-120/matched placebo only

- Azacitidine only
- Both AG-120/matched placebo and azacitidine

7.8.1.1. Adverse Events of Special Interest

The following are considered AESIs:

- QT prolongation (see “AG-120-specified Safety Search Criteria” for the criteria used to identify the relevant AEs)
- Leukocytosis (see “AG-120-specified Safety Search Criteria” for the criteria used to identify the relevant AEs)
- IDH differentiation syndrome (see “AG-120-specified Safety Search Criteria” for the criteria used to identify the relevant AEs)

Additional TEAEs of interest indicative of clinical benefit are as follows (see “AG-120-specified Safety Search Criteria” for the criteria used to identify the relevant AEs):

- Infection
- Bleeding

The following will be summarized for each AESI category and additional TEAEs of interest:

- AESIs/TEAEs of interest by PT
- AESIs/TEAEs of interest by PT and worst grade
- Grade ≥ 3 AESIs/TEAEs of interest by PT
- AESIs/TEAEs of interest leading to discontinuation of study drug by PT
- Serious AESIs/TEAEs of interest by PT
- AESIs/TEAEs of interest leading to death by PT

AESIs/TEAEs of interest leading to discontinuation of study drug will be summarized separately for:

- AG-120/matched placebo only
- Azacitidine only
- Both AG-120/matched placebo and azacitidine

7.8.1.2. Adverse Events Associated with COVID-19

The selection of AEs associated with COVID-19 will be based on the MedDRA MSSO list of PTs. The following will be summarized:

- TEAEs associated with COVID-19, by SOC and PT
- Grade ≥ 3 TEAEs associated with COVID-19, by SOC and PT
- Serious TEAEs associated with COVID-19, by SOC and PT

- TEAEs associated with COVID-19 leading to discontinuation of study drug, by SOC and PT
- TEAEs associated with COVID-19 leading to interruption of study drug, by SOC and PT
- TEAEs associated with COVID-19 leading to dose reduction, by SOC and PT
- TEAEs associated with COVID-19 leading to death, by SOC and PT

TEAEs associated with COVID-19 leading to discontinuation of study drug, leading to interruption of study drug, and leading to dose reduction will be summarized separately for

- AG-120/matched placebo only
- Azacitidine only
- Both AG-120/matched placebo and azacitidine

7.8.2. Death

The frequency of subjects in the safety analysis set who died, along with the cause of death, will be tabulated based on information from the Death Report eCRF. Cause of death will be summarized for the following categories:

- On-treatment death: Deaths within 28 days after the last dose of study treatment (ie, deaths during the on-treatment period)
- Post-treatment death: Deaths more than 28 days after the last dose of study treatment (ie, deaths after the end of the on-treatment period)
- Overall: All deaths

In addition, for each cause of death reported in the eCRF, those related to COVID-19 will be summarized.

Deaths for all screened subjects will be provided in a by-subject listing.

7.8.3. Clinical Laboratory Data

Clinical laboratory test results will be expressed in SI units.

For all laboratory tests (chemistry, hematology, coagulation), the actual values and the changes from baseline will be summarized by study visit.

For each laboratory test performed in the study, a by-subject listing of laboratory test results will be presented with the corresponding CTCAE grades (if applicable), laboratory normal ranges, and flags for values below lower limit of normal (LLN) or above upper limit of normal (ULN).

Parameters with CTCAE grades available:

Clinical laboratory test results will be graded according to CTCAE v4.03 as applicable. Grading will be derived based on the numerical thresholds defined by the CTCAE criteria. Non-numerical qualifiers will not be taken into consideration in the derivation of CTCAE grading.

Laboratory test results classified according to CTCAE will be described using the worst grade. For parameters graded with 2 separate toxicity criteria, such as potassium (hypokalemia/hyperkalemia), the toxicities will be summarized separately. Low direction toxicity (eg, hypokalemia) grades at baseline and postbaseline will be set to 0 when the variables are derived for summarizing high direction toxicity (eg, hyperkalemia), and vice versa.

The frequency of subjects with laboratory toxicities during the on-treatment period will be tabulated as follows. The denominator used to calculate percentages for each laboratory test is the number of subjects evaluable for CTCAE grading for that parameter (ie, those subjects for whom a Grade of 0, 1, 2, 3 or 4 can be derived).

- The summary of laboratory parameters by CTCAE grade will include the number and percentage of subjects with Grade 1, 2, 3, 4; Grade 3-4; and Any Grade (Grades 1-4) during the on-treatment period. The highest CTCAE grade during the on-treatment period is considered the worst grade
- The shift table will summarize baseline CTCAE grade versus worst CTCAE grade during the on-treatment period. The highest CTCAE grade during the on-treatment period is considered the worst grade
- Newly occurring or worsening laboratory abnormalities (Any Grade, Grade 3-4) during the on-treatment period will also be summarized

Parameters with CTCAE grades not available:

Results of laboratory tests that are not part of CTCAE will be presented according to the following categories: below the LLN, within normal limits, and above the ULN according to the laboratory normal ranges.

Shift tables will display the frequency of subjects with shifts from baseline missing, <LLN, normal, or >ULN to each of <LLN, normal or >ULN during the on-treatment period.

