10.6.5. Safety Laboratory Assessments

Clinical laboratory evaluations are to be performed by the site's local laboratory. Prior to starting the study, the Investigator will provide to the Sponsor (or its designee) copies of all laboratory certifications and normal ranges for all laboratory parameters to be performed by that laboratory.

Clinical laboratory evaluations are to be conducted according to the Schedule of Assessments (6). In addition, all clinically significant laboratory values will be further investigated according to the judgment of the Investigator.

The following safety laboratory parameters are to be evaluated by the Investigator:

Hematology: Hemoglobin, RBC count, WBC count with differential, ANC, platelet count, peripheral blast count

Chemistry: Sodium, potassium, calcium, magnesium, albumin, glucose, BUN, creatinine, lactate dehydrogenase, ALP, AST, ALT, total bilirubin, phosphate, bicarbonate

Coagulation Studies: Activated partial thromboplastin time (aPTT), INR

Blood for hematology and chemistries is to be obtained: at Screening; on Days 1, 8, 15, and 22 (± 3 days) of Cycle 1 (Weeks 1, 2, 3, and 4); on Days 1 and 15 (± 3 days) of Cycles 2, 3, and 4 (Weeks 5, 7, 9, 11, 13, and 15); on Day 1 (± 3 days) of each treatment cycle thereafter (Weeks 17+); at EOT; and at 4 weeks post-treatment. All blood samples for hematology and chemistries must be drawn prior to administration of study drugs.

Blood for coagulation studies is to be obtained at Screening, on Day 1 (± 3 days) of each treatment cycle, and at the EOT Visit.

Pregnancy Test: All women of reproductive potential must have a negative pregnancy test to be eligible. A serum β -hCG pregnancy test will be performed at Screening and must be confirmed negative within 72 hours prior to study treatment administration.

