12.6.3. Other Safety Data

Descriptive statistics of ECOG PS over time will be summarized by frequency. Shift tables may be provided for ECOG PS from baseline to worst value of post-baseline assessments.

Additional safety analyses may be performed if deemed necessary.

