6.3.4. Baseline

For efficacy evaluations, the last adequate assessment on or before the date of randomization will be used as the baseline. Per protocol, the first QoL assessment is planned to occur on Cycle 1 Day 1 before the start of study treatment. Therefore, for QoL assessments only, if there is no value available on or before the date of randomization, then the last measurement on or before the start of study treatment will be used as the baseline.

For summaries of baseline characteristics based on the FAS, baseline will be defined as follows:

- For subjects randomized and not dosed: the last assessment on or before the date of randomization
- For subjects randomized and dosed: the last assessment on or before the start of study treatment

For safety evaluations, the last assessment on or before the start of study treatment will be used as the baseline.

If, per protocol, an assessment is to be performed on study day 1, before the first dose of study treatment, and the assessment time, time of first dose of study treatment, or both, is missing (or not collected), it will be assumed that the assessment is performed before study treatment administration. Unscheduled assessments will be used in the determination of baseline; however, an unscheduled assessment on study day 1 will be considered to have been obtained after study treatment administration.

If no assessment meets the definition of baseline for an evaluation, the baseline will be set to missing.

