6.3.5. On-Treatment Period

The on-treatment period starts on the date of the start of study treatment and ends 28 days after the end of study treatment.

Data listings will include all assessments and events, with those that occur outside of the on-treatment period flagged.

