7.8.3.2. Chemistry

Liver function tests: Alanine aminotransferase (ALT), aspartate aminotransferase (AST), alkaline phosphatase (ALP), and total bilirubin are used to assess possible drug-induced liver toxicity. The ratios of test result to ULN will be calculated and categorized for these parameters during the on-treatment period.

The summary of liver function tests will include the following categories. The frequency of subjects with each of the following during the on-treatment period will be summarized by treatment arm:

- ALT $>3\times\text{ULN}$, ALT $>5\times\text{ULN}$, ALT $>10\times\text{ULN}$, ALT $>20\times\text{ULN}$
- AST $>3\times\text{ULN}$, AST $>5\times\text{ULN}$, AST $>10\times\text{ULN}$, AST $>20\times\text{ULN}$
- (ALT or AST) $>3\times\text{ULN}$, (ALT or AST) $>5\times\text{ULN}$, (ALT or AST) $>10\times\text{ULN}$, (ALT or AST) $>20\times\text{ULN}$
- Total bilirubin $>2\times\text{ULN}$
- Concurrent ALT $>3\times\text{ULN}$ and total bilirubin $>2\times\text{ULN}$
- Concurrent AST $>3\times\text{ULN}$ and total bilirubin $>2\times\text{ULN}$
- Concurrent (ALT or AST) $>3\times\text{ULN}$ and total bilirubin $>2\times\text{ULN}$
- Concurrent (ALT or AST) $>3\times\text{ULN}$ and total bilirubin $>2\times\text{ULN}$ and ALP $\geq 2\times\text{ULN}$
- Concurrent (ALT or AST) $>3\times\text{ULN}$ and total bilirubin $>2\times\text{ULN}$ and (ALP $<2\times\text{ULN}$ or missing)

Concurrent measurements are those occurring on the same date.

Categories will be cumulative, ie, a subject with an AST $>10\times\text{ULN}$ will also appear in the categories $>5\times\text{ULN}$ and $>3\times\text{ULN}$. Liver function test elevation and possible Hy's Law cases will be summarized using frequency counts and percentages.

An evaluation of Drug-Induced Serious Hepatotoxicity (eDISH) plot will be created, with different symbols for different treatment arms, by graphically displaying:

- Peak serum ALT (/ULN) vs peak total bilirubin (/ULN) including reference lines at ALT = $3\times\text{ULN}$ and total bilirubin = $2\times\text{ULN}$
- Peak serum AST (/ULN) vs peak total bilirubin (/ULN) including reference lines at AST = $3\times\text{ULN}$ and total bilirubin = $2\times\text{ULN}$

In addition, a listing of all total bilirubin, ALT, AST, and ALP values for subjects with a postbaseline total bilirubin $>2\times\text{ULN}$, ALT $>3\times\text{ULN}$, or AST $>3\times\text{ULN}$ will be provided.

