7.8.7. ECOG Performance Status

The ECOG PS shift from baseline to highest score during the on-treatment period will be summarized.

ECOG PS will be presented in a by-subject listing.

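### A pre-dose value on the first-dose day is both baseline and on-treatment record, so two SAP shift tables cannot show improvement and resolved abnormalities enter on-treatment counts

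*SAP*

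**What the plan says.** Four rules meet on the day of first dose.

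- **Baseline (SAP 6.3.4).** "For safety evaluations, the last assessment on or before the start of study treatment will be used as the baseline". For a scheduled Day 1 assessment with a missing time, "it will be assumed that the assessment is performed before study treatment administration". An unscheduled Day 1 assessment is taken as post-dose.
- **Window (SAP 6.3.5).** "The on-treatment period starts on the date of the start of study treatment and ends 28 days after the end of study treatment". SAP 6.3.2 defines the start of treatment as a date, without a clock time.
- **Day 1 measurements.** Protocol 10.6.5 states "All blood samples for hematology and chemistries must be drawn prior to administration of study drugs", and hematology and chemistry are scheduled on Cycle 1 Day 1. ECOG PS is scheduled on Day 1 of each cycle (Protocol 10.6.2). Protocol 9.7 requires Day 1 procedures to be finished before dosing, so this score is pre-dose too.
- **Summaries.** For graded laboratory tests, "The shift table will summarize baseline CTCAE grade versus worst CTCAE grade during the on-treatment period" (SAP 7.8.3). For liver tests, "The frequency of subjects with each of the following during the on-treatment period will be summarized by treatment arm" (SAP 7.8.3.2). For performance status, "The ECOG PS shift from baseline to highest score during the on-treatment period will be summarized" (SAP 7.8.7).

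Other passages use a different boundary. Protocol 12.6.3 has "Shift tables may be provided for ECOG PS from baseline to worst value of post-baseline assessments". The liver listing at the end of SAP 7.8.3.2 is limited to postbaseline elevations. Protocol 12.6.1 counts on-treatment from the first dose.

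**The concern.** A shift table and a worst-on-treatment count are meant to describe what happened after treatment began. If the pre-dose baseline value also sits inside the on-treatment window, it becomes one of the candidates for the worst value. Two things follow.

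First, the worst value cannot be better than baseline, so recovery cannot appear. This matters most for ECOG PS. A score of 2 is itself a qualifying criterion (Protocol 8.2, criterion 1b), so it will be present at baseline in some subjects. The SAP plans no ECOG summary apart from this shift and a listing.

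Second, an abnormality present only before the first dose is reported as an on-treatment finding. Eligibility sets no minimum neutrophil or platelet count. It also allows leukemia-related transaminases above 3×ULN, and bilirubin up to just below 3×ULN for Gilbert's disease or leukemia. Such values could enter the grade frequencies or the liver categories, including those used for possible Hy's Law cases.

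**Working it through.** The plan states no figure to reproduce, so the check is one of logic.

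**Notation.** Let b be the baseline grade, dated on the first-dose day, and p the worst grade at any later on-treatment assessment.

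- Rule as written: worst on-treatment = max(b, p).
- Post-baseline rule: worst = p.

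**Cell counts.** The SAP grades laboratory results 0 to 4, giving 5 × 5 = 25 (b, p) pairs. Protocol 8.2 limits ECOG at entry to 0–2. With later scores 0–4 for a living subject, that gives 3 × 5 = 15 pairs.

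| Summary | As written | Post-baseline only |
|---|---|---|
| CTCAE shift: improvement cells | 0 | 10 |
| CTCAE Any Grade: cells counted | 24 | 20 |
| CTCAE Grade 3-4: cells counted | 16 | 10 |
| Newly occurring or worsening: cells | 10 | 10 |
| ECOG shift: improvement cells | 0 | 3 |

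These are counts of possible cells, not of patients. Improvement requires max(b, p) < b, which is impossible. The newly-occurring-or-worsening row does not move, because max(b, p) > b exactly when p > b.

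**Example.** ECOG 2 before dosing on Day 1 and 1 at every later visit gives max(2, 1) = 2, shown as 2 to 2. The post-baseline rule shows 2 to 1.

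**Effect on a frequency.** For any threshold,

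reported rate = true post-baseline rate + q,

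where q is the share of subjects abnormal before dosing and normal at every later on-treatment sample. The arm difference changes by the difference between the two arms' values of q. The documents give no value of q for either arm.

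**Where the overlap has no effect.**

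- The LLN/ULN shift (SAP 7.8.3) goes from baseline to each on-treatment category, with no worst-value rule. A subject above ULN at baseline and normal later can still appear under normal.
- The by-visit summaries of actual values and change from baseline (SAP 7.8.3) do not use the window in this way.
- A baseline dated before the first dose lies outside the window. This covers a screening value, or a Day 1 sample taken early within the ±3-day visit window.

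**Internal inconsistency.** A subject with bilirubin above 2×ULN only in the Day 1 pre-dose sample is counted in the SAP 7.8.3.2 category table. The same subject does not meet the postbaseline criterion of the listing in that section on that value.

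**The case against.** The best defense is that the intended reading is clear enough. SAP 7.8.3 refers to baseline and postbaseline grades, SAP 7.8.3.2 has the postbaseline listing, and SAP 6.3.4 orders Day 1 records as before or after dosing. A programmer would probably exclude the baseline record by habit. That stands as a prediction of practice, but the SAP does not say so. The ordering in 6.3.4 serves only to choose the baseline. SAP 6.4.5 says worst-value summaries in the on-treatment period draw on both scheduled and unscheduled visits, without removing the baseline visit.

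Four stronger readings are tempting, and the documents do not support them.

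- *No shift table can show improvement.* The LLN/ULN shift can. The restriction applies to the CTCAE worst-grade and ECOG highest-score shifts, and only to subjects whose baseline falls on the first-dose date.
- *Emergent laboratory toxicity is obscured.* The separate newly-occurring-or-worsening table isolates it and is unaffected.
- *Arm differences are heavily diluted.* Suppose the true post-dose rates are 40% and 60%, and a share p0 is abnormal pre-dose, independently of the later course. The 20-point difference becomes 20 × (1 − p0), that is 14, 10 or 6 points at p0 = 30%, 50% or 70%. Correlation moves this either way: 17.5 points at p0 = 30% with correlation 0.9, and 5.5 at p0 = 70% with correlation 0.5. None of these inputs is in the documents. At p0 = 70%, independence requires 0.7 × 0.6 = 42% of one arm and 0.7 × 0.4 = 28% of the other to be abnormal before dosing and normal at every later sample. For cytopenias that is implausible: blood is drawn again on Days 8, 15 and 22 of Cycle 1, and Protocol 9.8.2.2 says azacitidine causes cytopenias particularly in the first 2 cycles.
- *The liver signal is widely contaminated.* The eligibility limits (bilirubin ≤2×ULN, AST and ALT ≤3×ULN) coincide with the lowest table cut-points. Only subjects admitted under the exceptions, or who worsened after screening, can exceed them pre-dose. A possible Hy's Law count needs both exceeded on the same date.

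**Conclusion.** The point holds in limited form. Followed literally, the SAP lets one pre-dose record serve as both baseline and on-treatment value. For subjects with a baseline on the first-dose date, the CTCAE worst-grade shift and the ECOG highest-score shift then cannot show improvement. Pre-dose abnormalities that later resolve are also counted in the on-treatment grade frequencies and liver categories. This is a stated rule that gives a wrong descriptive result and disagrees with other passages of both documents, so it goes beyond missing detail.

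The size depends on two quantities the documents do not give: the share of subjects whose baseline is dated on the first-dose day, and the share of abnormalities that clear at every later sample. The second is probably small for persistent cytopenias. The rule is the same in both arms, the tables concerned are descriptive, and no efficacy analysis or Type 1 error is touched. The correction should be made because it is cheap and the safety tables would otherwise contradict one another.

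**What to change.** State in SAP 6.3.5, and repeat in 7.8.3, 7.8.3.2 and 7.8.7, that the worst-grade frequencies, CTCAE shift, liver categories, eDISH plot and ECOG highest-score shift use on-treatment assessments after the baseline record. A Day 1 pre-dose value then serves as baseline only. This agrees with the liver listing in SAP 7.8.3.2 and with Protocol 12.6.1 and 12.6.3. The cost is one sentence and one programming condition, with no new data.

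A separate minor point concerns Protocol 12.6.3, which says ECOG PS over time will be summarized by frequency. SAP 7.8.7 keeps only the shift and a listing. Adding that table costs one output and would show performance status at each visit, including any recovery.
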